Fibrinogen increase - mg/dL	400 – 500	501 – 600	> 600	--
Fibrinogen decrease - mg/dL	150 – 200	125 – 149	100 – 124	< 100 or associated with gross bleeding or disseminated intravascular coagulation (DIC)

* The laboratory values provided in the tables serve as guidelines and are dependent upon institutional normal parameters. Institutional normal reference ranges should be provided to demonstrate that they are appropriate.

** "ULN" is the upper limit of the normal range.

Urine *	Mild (Grade 1)	Moderate (Grade 2)	Severe (Grade 3)	Potentially Life Threatening (Grade 4)
Protein	Trace	1+	2+	Hospitalization or dialysis
Glucose	Trace	1+	2+	Hospitalization for hyperglycemia
Blood (microscopic) – red blood cells per high power field (rbc/hpf)	1 - 10	11 – 50	> 50 and/or gross blood	Hospitalization or packed red blood cells (PRBC) transfusion

* The laboratory values provided in the tables serve as guidelines and are dependent upon institutional normal parameters. Institutional normal reference ranges should be provided to demonstrate that they are appropriate.

[figure not shown]
Contains Nonbinding Recommendations

[figure not shown]
IV. REFERENCES

[figure not shown]
1. National Cancer Institute Common Toxicity Criteria, April 30, 1999. (<http://ctep.cancer.gov/reporting/CTC-3.html>)
2. Division of AIDS Table for Grading Severity of Adult Adverse Experiences; August 1992. (http://rcc.tech-res-intl.com/tox_tables.htm)
3. The Brighton Collaboration. Finalized Case Definitions and Guidelines. (http://brightoncollaboration.org/internet/en/index/definition_guidelines.html)
4. HIV Vaccine Trials Network Table for Grading Severity of Adverse Experiences; September 18, 2002. (http://rcc.tech-res-intl.com/tox_tables.htm)
5. Division of AIDS Table for Grading the Severity of Adult and Pediatric Adverse Events, December 2004. (<http://www3.niaid.nih.gov/research/resources/DAIDSClinRsrch/PDF/Safety/DAIDSAEGgradingTable.pdf>)

[figure not shown]

Material Transfer Agreement (hereinafter referred to as the "MTA")

19.2 Appendix 2: Insurance certificate

## 1 List of Abbreviations

ADR	Adverse Drug Reaction
AE	Adverse Event
CI	Confidence Interval
CRF	Case Report Form
CV	Coefficient of Variation
DBL	Data Base Lock
FAS	Full Analysis Set
ID	Intradermal
IgG	Immunoglobulin G
IM	Intramuscular
IMP	Investigational Medical Product
MedDRA	Medical Dictionary for Regulatory Activities
PP	Per Protocol
PT	Preferred Term
SAE	Serious Adverse Event
SAF	Safety Analysis Set
SAP	Statistical Analysis Plan
SD	Standard Deviation
SOC	System Organ Class
SUSAR	Suspected Unexpected Serious Adverse Reaction
TEAE	Treatment Emergent Adverse Event
TO	Topical ocular

## 2 Introduction

The statistical analysis plan for the CHLM-02 is based on the final protocol version 5.1 dated 14DEC2020.

The SAP describes in detail the analyses to be conducted and highlights any deviations from the analysis described in the protocol (see section 8). Deviations from methods described in this SAP, if any, will be specified in the clinical trial report.

Before releasing data for final analysis, one or more data review and classification meeting will be held to review protocol deviations to classify subjects with respect to analysis populations. The product of the classification meetings will be a detailed description of the analysis populations, and the number and nature of unresolved data queries will also be reported.

The analysis is performed based on:

- The clinical database, which includes the electronic Case Report Forms (CRF)
- List of protocol deviations
- Analysis populations documented in the Data Base Lock minutes

Reporting of the trial will be after the date of last subject last visit.

## 3 Trial Characteristics

### 3.1 Trial Objectives

#### 3.1.1 Primary Objective

[figure not shown]
- To evaluate the safety of CTH522-CAF01 administered Intramuscular (IM) in different doses
- To evaluate the safety of non-adjuvanted CTH522 administered Topical ocular (TO) or Intradermal (ID) simultaneously with CTH522-CAF01 IM
- To evaluate the safety of CTH522-CAF09b administered IM

#### 3.1.2 Secondary Objectives

- To evaluate the serum Immunoglobulin G (IgG) antibody responses obtained after IM administration of CTH522-CAF01 in different doses
- To evaluate the serum IgG antibody responses obtained after TO or ID administration of non-adjuvanted CTH522 simultaneously with CTH522-CAF01 IM
- To evaluate the serum IgG antibody responses obtained after IM administration of CTH522-CAF09b
- To evaluate the serum IgG antibody response obtained after TO administration of non-adjuvanted CTH522 on Day 140

#### 3.1.3 Exploratory Objectives

- To evaluate the systemic and mucosal immunogenicity after vaccination with CTH522 with different adjuvants and administration routes

[figure not shown]

### 3.2 Trial Design

[figure not shown]
The trial is a phase I, double-blind, parallel, randomised, and placebo-controlled trial of the chlamydia vaccine, CTH522, in healthy adults. The trial will be conducted at Imperial College Healthcare NHS Trust, London, in the UK.

It is planned to randomly assign 66 subjects into 12 treatment groups in six Cohorts. Cohorts A-D investigate CTH522-CAF01 administered IM in two doses (85 µg and 15 µg). Cohort E investigates CTH522-CAF09b administered IM in one dose (85 µg). Cohort F is the placebo group (Figure 1). The enrolled subjects will complete 12 trial visits.

**Figure 1: Trial design**

IM=intramuscular injection with CTH522-CAF01 or CTH522-CAF09b 85 µg or 15 µg; ID=intradermal injection with non-adjuvanted CTH522 24 µg; TO=topical ocular with non-adjuvanted CTH522 12 µg in each eye

**Table 1: Flow chart**

Trial visit (V)	1	2	3	4	5	6	7	8	9	10	11	12
Trial day	-	0	14	28	42	56	112	126	140	143	154	238
Windows (days)	-90 to -1	0	V2 + 12-16	V2 + 26-30	V4 + 12-16	V4 + 26-30	V4 + 77-91	V7 + 12-16	V7 + 26-30	V9 + 2-4	V9 + 12-16	V9 + 91-105
Informed consent	X											
Med. hist+demographics	X											
In-/exclusion criteria	X	X										
Blood for hep B and C, HIV, syphilis	X											
PCR for C. Trachoma and gonorrhoea infection 	X											X
Urinary pregnancy test	X	X		X			X		X			X
Physical examination	X											X
Eye exam including retina*	X*				X			X			X	
Eye exam**	X	X		X	X	X	X	X	X	X	X	X
Record weight/height	X											
Vital signs 	X	X	X	X	X		X	X	X	X	X	X
Concomitant medication	X	X	X	X	X	X	X	X	X	X	X	X
Randomisation		X										
Vaccination and route		1 IM		2 IM ID TO			3 IM ID TO			4 TO		
Issue diary card		X		X			X		X			
Review diary card			X		X			X		X	X	
Symptom-directed PE		X	X	X	X	X	X	X	X	X	X	X
Record adverse events	X	X	X	X	X	X	X	X	X	X	X	X
Safety lab 	X*	X*	X*	X*	X*		X*	X*	X*		X*	X*
Serum IgG ELISA 		X	X	X	X	X	X	X	X		X	X
Serum IgA ELISA+anti-CTH522 IgG subtypes + neutralising ab 		X	X	X	X	X	X	X	X		X	X
Ocular anti-CTH522 IgG + IgA ELISA (strip)		X		X	X	X	X	X	X	X	X	X
T- and B-cell Elispot frozen PBMCs 		X	X	X	X	X	X	X	X		X	X
ICS flow frozen PBMCs 		X	X	X	X	X		X	X		X	X
Transcriptional analysis frozen PBMCs 		X						X			X	
End-of-trial												X

ID=intradermal; IM=intramuscular; PE=physical examination; TO=topical ocular; V=visit

\*A biomicroscopy (e.g. via slit lamp examination), examining all areas of the eye including the retina which can be performed by a specialist at an eye clinic. If this procedure cannot be performed at V1, it is acceptable at V2 as long as it is performed prior to the first vaccination.

\*\*Eye examination not involving fundoscopy or any other examination modality that necessitates unacceptable prolonged closeness between examiner and participant or where the examination cannot be performed using standard personal protective equipment for examiner and participant.

[figure not shown]
single urine PCR tests for *C. Trachoma* and gonorrhoea; blood pressure, heart rate and oral temperature; taken pre-vaccination when scheduled at vaccination visits (V2, V4, V7 and V9); Safety lab: renal urea and electrolytes (sodium, potassium, chloride, urea, and creatinine); liver function tests (alanine aminotransferase, alkaline phosphatase, total bilirubin, total protein, albumin); full blood count (WBC, lymphocytes, monocytes, eosinophils, neutrophils, basophils, RBC, HGB, 'HCT, and platelets); total blood for safety: approximately 13 ml; total blood for safety: approximately 8 ml; amount of blood: approximately 1 x 10 ml; amount of blood in heparin tubes: 5 x 6 ml; amount of blood in heparin tubes: 2 x 6 ml

### 3.2.1 Treatment labels

The cohort labels will be used as treatment labels in tables, figures, and listings as described in Table 2. Cohorts who had the same treatment at first, second and/or third vaccination will when relevant be grouped at timepoints where the treatments received were similar, and will be labelled accordingly:

**Table 2: Treatment labels**

Day and treatment	Cohort	Label
Day 0		
85 µg IM CTH522-CAF01	A1, A2, B1, B2, C1, C2	Cohort A-C CTH-01-all
15 µg IM CTH522-CAF01	D1, D2	Cohort D CTH-01-low
85 µg IM CTH522-CAF09b	E1, E2	Cohort E CTH-09
IM Placebo	F1, F2	Cohort F Placebo
Day 28 and 112		
85 µg IM CTH522-CAF01 + ID Placebo	A1	Cohort A1 CTH-01+ID-PCB
85 µg IM CTH522-CAF01 + TO Placebo	A2	Cohort A2 CTH-01+TO-PCB
85 µg IM CTH522-CAF01 + TO CTH522	B1, B2	Cohort B CTH-01+TO
85 µg IM CTH522-CAF01 + ID CTH522	C1, C2	Cohort C CTH-01+ID
15 µg IM CTH522-CAF01 + TO Placebo	D1	Cohort D1 CTH-01-low+TO-PCB
15 µg IM CTH522-CAF01 + ID Placebo	D2	Cohort D2 CTH-01-low+ID-PCB
85 µg IM CTH522-CAF09b + TO Placebo	E1	Cohort E1 CTH-09+TO-PCB
85 µg IM CTH522-CAF09b + ID Placebo	E2	Cohort E2 CTH-09+ID-PCB
IM Placebo + TO Placebo	F1	Cohort F1 Placebo+TO-PBO
IM Placebo + ID Placebo	F2	Cohort F2

Placebo+ID-PCB		
Day 140		
85 µg IM CTH522-CAF01 + ID Placebo + TO Placebo	A1	Cohort A1 CTH-01+ID-PCB+TO-PCB
85 µg IM CTH522-CAF01 + TO Placebo + TO CTH522	A2	Cohort A2 CTH-01+TO-PCB+TO
85 µg IM CTH522-CAF01 + TO CTH522 + TO Placebo	B1	Cohort B1 CTH-01+TO+TO-PCB
85 µg IM CTH522-CAF01 + TO CTH522	B2	Cohort B2 CTH-01+TO
85 µg IM CTH522-CAF01 + ID CTH522 + TO placebo	C1	Cohort C1 CTH-01+ID+TO-PCB
85 µg IM CTH522-CAF01 + ID CTH522 + TO CTH522	C2	Cohort C2 CTH-01+ID+TO
15 µg IM CTH522-CAF01 + TO Placebo	D1	Cohort D1 CTH-01-low+TO-PCB
15 µg IM CTH522-CAF01 + ID Placebo + TO CTH522	D2	Cohort D2 CTH-01-low+ID-PCB+TO
85 µg IM CTH522-CAF09b + TO Placebo	E1	Cohort E1 CTH-09+TO-PCB
85 µg IM CTH522-CAF09b + ID Placebo + TO CTH522	E2	Cohort E2 CTH-09+ID-PCB+TO
IM Placebo + TO Placebo	F1	Cohort F1 Placebo+TO-PCB
IM Placebo + ID Placebo + TO Placebo	F2	Cohort F2 Placebo+ID-PCB+TO-PCB

The full treatment will be explained in footnotes. In the above CTH-01 is an abbreviation for CTH522-CAF01, and CTH-09 for CTH522-CAF09b.

### 3.3 Subjects included

[figure not shown]
It is planned to screen approximately 110 subjects to randomise 66 subjects. The subjects should be healthy male and female volunteers aged 18–45 years.

No sample size calculations have been made. The sample size is considered adequate for review of the safety profile of the described interventions for a phase I trial.

Number of randomised subjects to each treatment group is presented in Figure 1 above.

## 4 Analysis Populations

The following 3 analysis sets are defined:

- Safety analysis set (SAF): The SAF consist of all subjects randomised and exposed to the investigational medical products (IMPs), including subjects who are withdrawn after exposure to the IMP.
- Full analysis set (FAS): FAS will include subjects with observed data for all randomised subjects.
- Per Protocol (PP) analysis set: PP analysis set will include subjects who completed the trial without deviations judged to influence the primary endpoints. Please refer to section 4.1 for details.

Since all randomised subjects have observed data, FAS will consist of all randomised subjects.

The basis for safety analysis is the SAF. The analysis of all safety endpoints will be based on the SAF, and the subjects will be evaluated according to actual treatment.

The analysis sets will be defined at the data release meeting, which will take place prior to unblinding of the trial.

#### 4.1 Major protocol deviations

Before data base lock (DBL) all protocol deviations will be evaluated. Protocol deviations having a major impact on the co-primary endpoints will be identified and lead to exclusion from PP. The decisions will be documented.

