## 5.4 Baseline Characteristics and Demographics

Baseline characteristics and demographics consist of age, gender, race, weight, height, and BMI.

Demographics will be summarized using descriptive statistics. Age and gender will in addition be summarised for FAS and PP.

All information will be listed.

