## 7 Statistical Methodology for Primary and Secondary Endpoints

### 7.1 Analysis and Presentation of the co-Primary Safety Endpoints

The co-primary endpoints are:

- Solicited local injection site reactions after ID and/or IM administration of the vaccines: erythema, pruritus, pain, tenderness, swelling, and warmth occurring up to and including 14 days after any IMP administration
- Solicited local reactions after TO administration of the vaccine: watering eyes, swelling of eyelid, eye redness, and eye discomfort occurring up to and including 14 days after any IMP administration
- Solicited systemic reactions after IM and/or ID administration of the vaccines: oral temperature  $> 38.3^{\circ}\text{C}$ , chills, myalgia, and rash occurring up to and including 14 days after any IMP administration
- Any other adverse events (AEs)

These are collected in the subjects' diaries.

The primary analyses will be carried out for the SAF.

AEs will be coded using the Medical Dictionary for Regulatory Activities (MedDRA) version 22.1 - Sep 2019. AEs will be regarded as treatment emergent AEs (TEAEs) if they occur after administration of randomised treatment.

Only TEAEs will be summarised. The summaries will include number of events, number of subjects, and proportion of subjects reporting these events.

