#### 7.1.1 Solicited injection site reactions

Solicited injection site reactions after IM and/or ID administration are defined as AEs with the following PTs:

- Injection site erythema
- Injection site pruritus
- Injection site pain (covers both the lower level terms *injection site tenderness* and *injection site pain*)
- Injection site swelling
- Injection site warmth

occurring in the period after and up to and including 14 days after Day 0, Day 28, and Day 112 vaccination.

The number and percentage of subjects and the number of events will be presented by PT:

- At Day 0 for the four treatment regimens present

- Cohort A-C
- Cohort D
- Cohort E
- Cohort F
- At Day 28 and Day 112 for the 10 treatment regimens present
  - Cohort A1
  - Cohort A2
  - Cohort B
  - Cohort C
  - Cohort D1
  - Cohort D2
  - Cohort E1
  - Cohort E2
  - Cohort F1
  - Cohort F2

The number and percentage of subjects with events occurring in the period after and up to and including 14 days after the Day 0 vaccination and the corresponding 95% CI will be presented together with a pairwise comparison of number of subjects with events using Fishers exact test for the following:

- Cohort A-C vs Cohort D
- Cohort A-C vs Cohort E
- Cohort A-C vs Cohort F

All information will be listed.

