#### 7.1.4 Any other AEs

Any other AEs are all TEAEs not included in the above three sections.

The number and percentage of subjects and the number of events will be presented by system organ class (SOC) and preferred term (PT) for the following timespans:

- From Day 0 vaccination to before Day 28 vaccination for the four treatment regimens present
  - Cohort A-C
  - Cohort D
  - Cohort E
  - Cohort F
- From Day 28 vaccination to before Day 112 vaccination and
- From Day 112 vaccination to before Day 140 vaccination

The immediate above two tables will include the nine treatment regimens present, where the placebo cohort (F) will be regarded as one

- Cohort A1
  - Cohort A2
  - Cohort B
  - Cohort C
  - Cohort D1
  - Cohort D2
  - Cohort E1
  - Cohort E2
  - Cohort F
- From Day 140 vaccination to end of trial for the 11 treatment regimens present, where the placebo cohort (F) will be regarded as one
  - Cohort A1
  - Cohort A2
  - Cohort B1
  - Cohort B2
  - Cohort C1
  - Cohort C2
  - Cohort D1
  - Cohort D2
  - Cohort E1
  - Cohort E2
  - Cohort F

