## 7.3 Analysis and Presentation of the Secondary Immunogenicity Endpoint

The secondary immunogenicity endpoint is seroconversion for anti-CTH522 IgG antibody at any time points after vaccinations.

All immunogenicity endpoints will be analysed using the FAS and the subjects will be evaluated according to the actual treatment received. The PP analysis set will be used as supportive.

[figure not shown]

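### The per-protocol set supports only the IgG analysis, but subjects enter it by completing the trial and by deviations judged against the safety endpoints

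*SAP*

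**What the plan says.** SAP section 4 defines the set: "PP analysis set will include subjects who completed the trial without deviations judged to influence the primary endpoints". Section 4.1 turns this into an exclusion rule: "Protocol deviations having a major impact on the co-primary endpoints will be identified and lead to exclusion from PP". Section 7.1 lists the co-primary endpoints: three groups of solicited reactions and any other adverse events. None concerns antibodies.

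The sets are assigned as follows. For safety, section 4 states "The analysis of all safety endpoints will be based on the SAF", and section 7.1 repeats for the co-primary endpoints "The primary analyses will be carried out for the SAF". For immunogenicity, section 7.3 uses FAS as the main set and adds "The PP analysis set will be used as supportive". Exploratory immunogenicity goes to a separate report (section 7.4), so the immunogenicity analysed under this SAP is anti-CTH522 IgG. PP otherwise appears only as a count in the disposition table (section 5.2), in the handling of deviations (section 5.3), and in a demographic summary: "Age and gender will in addition be summarised for FAS and PP".

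SAP sections 2, 4 and 5.3 leave the classification of subjects and deviations to meetings held before unblinding.

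**The concern.** A PP analysis is meant to show whether a result holds once subjects with deviations that matter for that result are set aside. Here the filter is built for endpoints that PP never analyses and is silent on the one it does. It can therefore err in both directions: keep a subject whose titre is affected, and drop a subject whose titre is sound.

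PP is also the only planned restriction of the IgG data for timing deviations. SAP section 4 says FAS will be all randomised subjects, so FAS removes nobody for a deviation. Section 5.1 lets the first later unscheduled visit stand in for an unavailable scheduled one, so a late titre can enter a FAS visit summary. If PP does not screen for timing, no planned analysis does.

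**Working it through.** The documents state no figure to reproduce. The check compares the entry rule with the endpoint, using the SAP flow chart (Table 1).

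**1. What the rule tests and what PP analyses**

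| | Tested at PP entry | Analysed on PP |
|---|---|---|
| Solicited reactions, other AEs | Yes (SAP 4, 4.1) | No, SAF only (SAP 4, 7.1) |
| Trial completion, Day 238 | Yes (SAP 4) | Not an endpoint |
| Anti-CTH522 IgG | No | Yes, supportive (SAP 7.3) |

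**2. Deviations the rule need not exclude**

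- *Late serum sample.* The Day 126 visit must fall 12 to 16 days after the third vaccination visit. Injection site reactions count when "occurring in the period after and up to and including 14 days after Day 0, Day 28, and Day 112 vaccination". That window is anchored to vaccination, so the date of a blood draw enters no reaction definition. A mistimed sample is a recorded deviation (SAP 5.3 lists visits out of window), but it has no evident route to a major impact on a safety endpoint.
- *Late third vaccination.* The permitted interval is 77 to 91 days after the second vaccination visit. If it is exceeded, the 14-day reaction window moves with the injection. For other adverse events the period is "From Day 28 vaccination to before Day 112 vaccination", which simply becomes longer. For antibodies the interval matters by design: Protocol section 9.2.1 explains the same prime-boost spacing in the previous trial by the time needed for affinity maturation.

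**3. Subjects the rule removes although their titres are valid**

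- The Wilcoxon tests in SAP 7.3.1 are at Day 28 and Day 126. Completion is at Day 238, which is 238 − 28 = 210 and 238 − 126 = 112 days later.
- Table 1 schedules serum IgG at V2 (baseline), V3 to V9, V11 and V12, so there are 9 post-baseline samples. V3 to V8, up to Day 126, are 6 of 9 = 67%.
- A subject who leaves after Day 154 has given 8 of 9 samples = 89%, including the first scheduled titre after the Day 140 dose, and is still outside PP at every time point.
- In the cumulative summary (SAP 7.3.1) a seroconverted subject counts at all later visits, so completion is not needed to establish that status.

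These counts describe the schedule. They do not measure bias.

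**The case against.** The strongest reply is that the blinded review will settle this. SAP section 2 promises a detailed description of the analysis populations. Section 5.3 has deviations classed as major or minor, includes a laboratory type, and does not confine the judgement to safety. A reader might therefore infer from this point that the meetings are barred from applying an IgG criterion. The documents do not support that: the meetings could apply one. What stands is that section 4.1 gives the only stated test, and that test is impact on the co-primary endpoints.

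A reader might also infer that IgG-relevant deviations in general slip through. That goes too far. Subjects given incorrect treatment are presented separately (SAP 5). A missing sample adds nothing to its visit, because observed cases are used without imputation (SAP 5.1, 7.6). Missed vaccinations and prohibited medication may well be excluded on safety grounds. The clear gap is the timing of samples and vaccinations.

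Requiring completion is not arbitrary: IgG is summarised to Day 238, other adverse events are followed to the end of the trial, and one fixed set is simpler than sets that change by visit. This is a fair defence for the late visits, but not for comparisons at Day 28 and Day 126.

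Section 7.3 does not list the outputs to be repeated on PP, but its natural reading is that the FAS analyses are repeated. That is at most a missing detail.

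**Conclusion.** The point holds as a mismatch between the PP rule and the one endpoint analysis PP serves. It deserves correction before unblinding, but its reach is small: a supportive analysis of a secondary endpoint. FAS and safety results do not change.

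No size can be given. The documents state no deviation or dropout rate and no sample size calculation, and the cohort sizes are in Figure 1, which was not available for this check. In the previous trial all actively vaccinated subjects reached 4-fold seroconversion (Protocol section 6). If that recurs among subjects with titres, PP membership cannot alter the 4-fold percentage in the active cohorts.

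A reader might infer that one misplaced subject would overturn a PP test. The documents do not show this. Assume 12 subjects per cohort (0.91 × 66 ≈ 60 active subjects, 60/5 = 12 if split equally) and an exact two-sided Wilcoxon test without ties that is only just significant: U = 37, p = 0.045. One subject contributes on average 37/12 = 3.08 to U. With 11 against 12, removing 3 gives U = 34, p = 0.051; removing 4 gives U = 33, p = 0.044. Whether 0.05 is crossed depends on the assumed sizes, the borderline start and the rounding, so this is no estimate of effect.

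A separate minor point: Protocol section 11.4 says both that the primary endpoints rest on SAF and that the primary analysis is carried out on SAF, FAS and PP. The SAP uses SAF and does not mention this in section 8. This may explain why the PP wording refers to the primary endpoints, but the documents do not say so, and it adds nothing to the weight of this point.

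**What to change.** In SAP sections 4 and 4.1, before unblinding and at the latest at the data release meeting:

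- For the immunogenicity analysis, base PP exclusion on deviations judged at blinded review to affect the IgG response or its sampling: mainly vaccination and sample timing, missed vaccinations and prohibited medication.
- Do not require trial completion for the Day 28 and Day 126 comparisons.

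Adding the IgG endpoint to the section 4.1 criterion would deal with the timing deviations alone; the completion requirement needs its own sentence. One line in section 7.3 naming the outputs repeated on PP would be a useful clarification.

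The cost is SAP wording and a little more work at the blinded review. PP numbers may differ by visit, so each table should show its own. No new data are needed.
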